16.5 Planned subgroup analyses

Subgroup analyses will be performed to the same variables used in the minimisation algorithm (except site/hospital) (see Section 6.5 – ENROLMENT, RANDOMISATION and BLINDING) and performed on the primary outcome only. The effects of these subgroups will be examined by including an intervention group by subgroup interaction parameter in the regression model, which will be presented alongside the effect estimate and 95% confidence interval within subgroups. The results of subgroup analyses will be treated with caution and will be used for the purposes of hypothesis generation only. Any other subgroup analysis which are not part of the variables used in the minimisation algorithm will be defined ahead of database lock in the Statistical Analysis Plan.

16.6 Missing data and sensitivity analyses

Every attempt will be made to collect full follow-up data on all study patients; it is thus anticipated that missing data will be minimal. Since the primary outcome is based on a time-to-event analysis, a sensitivity analysis to assess the impact of missing data will not be required since all patients will be included in the analysis and will be censored at the point where they have no further data.

There may be times when patients in both groups do not sufficiently adhere to their treatment, i.e. poor uptake of the drug, or may even be commenced on an alternative drug. To assess the impact of this, a per-protocol analysis for the primary outcome will be undertaken as a sensitivity analysis.

Full details will be included in the Statistical Analysis Plan.

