If face-to-face consent is not possible, remote written consent may be undertaken. The informed consent discussions will proceed as above but by telephone, videoconference or equivalent. This written process will be undertaken in the presence of a witness who will initial the boxes on the ICF in response to discussions between the member of the research team and the legal representative. The member of the research team will then sign and date the ICF as will the witness. A copy of the completed ICF will be given to the patient and can be provided to the legal representative upon request. As above, a copy of the ICF will also be filed in the patient's medical notes, a copy will be sent to BCTU and the original placed in the ISF.

Should the legal representative decide that the patient would not want to take part, the patient will be withdrawn from the trial and no further data collected.

If the patient does regain capacity during the follow-up period, they will be asked to give consent for themselves using the process outlined in Section 5.1.

The patient's wishes (consent or refusal) will in all cases, supersede the legal representative's consent.

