5.3 Patients who do not survive

The most challenging ethical consideration in this trial relates to the inevitable death of some patients. Actively seeking out and informing relatives of trial participation is transparent and avoids potential distress were the family to discover at some future point that their relative had been involved in a clinical trial. However, informing the relatives/ friends of trial participation in the immediate aftermath of their relative/ friend's death will impose an additional emotional burden at a time of great distress. Previous and ongoing critical care trials have used passive information approaches, placing information in publicly accessible locations and in sites likely to be visited by relatives of the deceased (hospitals, GP surgeries, the offices of the Registrars of Births and Deaths). Such information contains brief details of the trial and contact details for those wishing to seek further information. This allows a relative to make an individual decision as to whether to seek further information regarding their relative/ friend, at a time of their choosing. This is the approach that we will take with the ABBRUPT trial and a REC approved poster will be placed in appropriate locations of participating sites.

Whilst every effort should be made to obtain consent as soon as possible following randomisation, there remains a risk that a patient may die prior to consent being obtained. In this instance, only a minimal, pseudoanonymised (trial number and age) dataset comprising of variables captured as part of standard of care will be transferred to BCTU. A Change of Status Form will also be completed for these patients.

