10 WITHDRAWAL AND CHANGES IN LEVELS OF PARTICIPATION

Informed consent is defined as the process of learning the key facts about a clinical trial before deciding whether or not to participate. It is a continuous and dynamic process and patients should be asked about their ongoing willingness to continue participation at all visits. Patients should be aware from the beginning that they can freely withdraw (cease to participate) from the trial at any time. A patient may wish to cease to participate in a *particular* aspect of the trial.

Patients found to be ineligible post-randomisation (i.e. they were eligible at the point of randomisation but became ineligible over the course of the trial) should be followed up according to all trial processes and will still have their data analysed unless they explicitly change their level of participation.

The changes in levels of participation within the trial are categorised in the following ways:

No trial intervention: The patient would no longer like to receive the trial intervention but is willing to be followed up in accordance with the schedule of assessments (i.e., the patient has agreed that data can be collected and used in the trial analysis).

No trial related follow-up: The patient does not wish to attend trial visits in accordance with the schedule of assessments but is willing to be followed up at standard clinic visits (i.e., the patient has agreed that data can be collected at standard clinic visits and used in the trial analysis).

No further data collection: The patient is not willing to be followed up in any way for the purposes of the trial AND does not wish for any further data to be collected (i.e., only data collected prior to any changes of levels in participation can be used in the trial analysis).

The details of changes of levels in participation within trial (date, reason and category of status change) should be clearly documented in the source documents.

The Legal Representative and/or Researcher are also able to withdraw the patient for the above reasons.

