16 STATISTICAL CONSIDERATIONS

16.1 Sample size

Sample size calculation is based on a time-to-event superiority analysis. Literature (8) suggests that 90-day mortality in patients with NOAF was approximately 20%. A 5% absolute difference in mortality is considered a 'meaningful clinically important difference [MCID]' which equates to a hazard ratio of approximately 0.73. Using 90% power and a 2-sided alpha of 0.05 to detect a hazard ratio of 0.73 with event rate of 20% (or survival rate of 80%), a total of 426 events will be required. The enrolment of approximately 2430 patients would provide the required number of primary outcome events. Allowing for a 5% non-evaluable rate, a total of 2560 patients (1280 per group) will need to be recruited (rounded to nearest 10). We have allowed for a slightly higher non-evaluable rate as this study is recruiting critically ill patients undergoing an acute deterioration during their care.

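### Section 16.6 rules out a missing-data sensitivity analysis for 90-day mortality because everyone is included and censored, but that does not make loss to follow-up harmless

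*Protocol*

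**What the plan says.** **Analysis.** Section 16.3 compares time to death from any cause with a Cox model. Section 16.2 adjusts for age band and takes hospital as a random effect. Section 16.6 expects little missing data and states that "a sensitivity analysis to assess the impact of missing data will not be required since all patients will be included in the analysis", with censoring at the last available data. The only sensitivity analysis it names for the primary outcome is per-protocol. It refers to the SAP for full details.

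**Expected loss.** Section 16.1: "Allowing for a 5% non-evaluable rate, a total of 2560 patients (1280 per group) will need to be recruited". It describes this rate as slightly raised because the patients are critically ill. In the pilot criteria (Sections 2.1 and 8.1), drop-out is green below 5% and amber from 5% to 10%, and completeness of the primary outcome is green from 90%.

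**Routes to loss.** Treatment is open label (Section 6.6). Consent is sought after randomisation, with a 72-hour target where a representative is needed (Section 5.2). If the representative decides that the patient would not want to take part, "the patient will be withdrawn from the trial and no further data collected". Section 5.3 accepts that "there remains a risk that a patient may die prior to consent being obtained"; a minimal dataset is kept for those patients. Section 10 defines three levels of reduced participation and adds: "The Legal Representative and/or Researcher are also able to withdraw the patient for the above reasons".

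**The concern.** Keeping every randomised patient in a time-to-event analysis and censoring those who leave does not remove the missing-data problem. It replaces it with an assumption: at each time, patients who leave have the same later risk of death as patients of the same age band and hospital who stay. The planned analysis neither tests this nor varies it. The per-protocol analysis deals with adherence, which is a different question.

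The assumption needs examining here because refusal comes after allocation is known and treatment has started. Refusal could be related to how the patient is doing, and it could differ between arms. If both happen, the primary hazard ratio and the Kaplan-Meier curves would be biased in a direction that cannot be predicted. The protocol has ruled out beforehand the analysis that would show whether the conclusion withstands this, and one added after the results are known would look post hoc.

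Sections 16.1 and 16.6 also pull apart. One allows for 5% of patients being non-evaluable; the other says that everyone is in the analysis and that missing data will be minimal.

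**Working it through.** **1. The design figures reproduce.** Section 16.1 says "A 5% absolute difference in mortality is considered a 'meaningful clinically important difference [MCID]' which equates to a hazard ratio of approximately 0.73" and "a total of 426 events will be required", with 90% power and two-sided alpha 0.05.

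- HR = ln(0.85)/ln(0.80) = 0.728.
- Schoenfeld formula at HR 0.73: 425 events. Freedman formula at HR 0.7283: 426 events.
- Patients: 426/0.175 = 2434, where 0.175 is the mean of 20% and 15%; the plan has about 2430. Then 2430/0.95 = 2558, rounded to 2560.
- Power at 426 events is 0.901.

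**2. Size of the allowance.** 0.05 × 2560 = 128 patients, 64 per arm, leaving 1216 per arm. At the design effect those 1216 give about 243 v 182 deaths, a difference of 61. With 426 events, a just-significant HR is exp(−1.96 × 2/√426) = 0.827.

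**3. Tipping points.** These assumptions are not in the protocol: equal numbers lost per arm; 20% mortality in the higher-mortality arm; and 20% among that arm's lost patients. That arm therefore has 0.20 × 1280 = 256 deaths. In the other arm, with observed mortality p, m lost patients and mortality q among them:

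- D2 = p × (1280 − m) + q × m
- log HR = ln[ ln(1 − D2/1280) / ln(0.80) ], SE = √(1/256 + 1/D2)

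Two-sided p reaches 0.05 at D2 of about 217.5. Check: 217.5/1280 = 0.170; HR = ln(0.830)/ln(0.80) = 0.835; log HR = −0.181; SE = 0.092; z = −1.96. So q = (217.5 − p × (1280 − m))/m. The hazard multiple is ln(1 − q)/ln(1 − p).

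| Loss per arm | Observed mortality | HR | p-value | q at which significance is lost | Multiple of that arm's hazard |
|---|---|---|---|---|---|
| 64 (5%) | 20% v 15% | 0.73 | 0.001 | 55% (35 of 64) | 4.9 |
| 64 (5%) | 20% v 16% | 0.78 | 0.010 | 36% (23 of 64) | 2.6 |
| 64 (5%) | 20% v 16.5% | 0.81 | 0.026 | 26% (17 of 64) | 1.7 |
| 64 (5%) | 20% v 16.7% | 0.82 | 0.036 | 23% (14 of 64) | 1.4 |
| 128 (10%) | 20% v 15% | 0.73 | 0.002 | 35% (45 of 128) | 2.7 |

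A two-proportion z-test gives nearly the same points (for example 36 of 64 in the first row).

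**4. A 30-point gap among the lost, at the design effect.** Take 50% v 20% mortality among the 64 lost per arm. D2 = 0.15 × 1216 + 0.50 × 64 = 214.4, against 256, and z is about 2.12. The result stays significant.

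**5. Loss that is informative but equal in both arms.** With 5% lost per arm at 0.5 to 3 times the hazard of those followed, the HR is 0.725 to 0.728 against a true 0.728, and power is 0.89 to 0.91. Material bias needs a difference between arms.

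**The case against.** **The bias is not demonstrated.** A reader might infer that deferred consent makes censoring informative by design, since early deaths are kept and refusers leave alive. The documents do not support that. Only living patients can be censored in any survival analysis, and time before refusal stays in the risk set. Bias in the hazard ratio needs refusers to have a different later risk from comparable patients, and needs this to differ by arm. The protocol gives no refusal rate, no rate by arm and no link to prognosis. This objection stands, so the point is about an untested assumption.

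**The numbers are less alarming than they look.** A reader might set 64 lost per arm beside the 61-death design difference and conclude that the planned loss is enough to overturn the result. As a count it is, but only if nearly all the lost patients in one arm die and nearly none in the other. The 5% is also a sizing allowance for every kind of non-evaluable patient, so it does not forecast refusals. This stands for a result at the design effect; it does not protect an observed HR of about 0.78 to 0.82.

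**There are safeguards.** Mortality status is collected at ICU discharge, hospital discharge, day 60 and day 90, the last two remotely if needed. Transferred patients have a data route, and drop-out and completeness are pilot criteria. These limit loss but do not show what remaining loss does to the estimate.

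**The SAP will give details.** Leaving methods to the SAP is normal. Here, however, the protocol has made the decision and given its reason, and the referral to the SAP does not reopen it.

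**Withdrawal rules.** A reader might take Section 10 to let an unblinded researcher end data collection at will. That is one reading of an ambiguous sentence: each level is defined by what the patient wishes, and the levels are already extended to the representative. The text needs clarifying, but the main point does not depend on it.

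**Conclusion.** The point holds in a limited form. The reason in Section 16.6 is wrong, the analysis it excludes is relevant to the primary outcome, and the statement does not fit the 5% allowance in Section 16.1.

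At the design effect with 5% loss, the conclusion is fairly robust: significance is lost only at about 55% v 20% mortality among the lost. It is fragile for smaller significant effects (1.4 to 2.6 times the arm's hazard for observed HRs of 0.82 to 0.78), and less robust at the design effect if loss reaches 10% (2.7 times). The 10% is a scenario: it lies at the edge of the green completeness band and the top of the amber drop-out band, and is not a forecast. All these figures rest on the assumptions in step 3 of the working.

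Neither actual bias nor its direction is shown. Sample size, power and the choice of primary estimator are unaffected. This should be fixed, but it does not invalidate the design.

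**What to change.** 1. In Section 16.6, delete the sentence saying that no missing-data sensitivity analysis is needed.
2. Pre-specify one sensitivity analysis of the primary outcome for patients censored before day 90: delta-adjusted or tipping-point, with the post-censoring hazard varied separately in each arm. Technical detail can go in the SAP.
3. Report censoring before day 90 by arm, time and reason.
4. Reconcile the statement that everyone is included with the 5% non-evaluable allowance in Section 16.1, by saying who counts as non-evaluable and how such patients enter the Cox model.

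The cost is a small amount of extra analysis and a few sentences; no extra patients are needed.

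Separately, Sections 5.2 and 10 should be reconciled on which participation levels apply when a representative refuses and when a researcher initiates withdrawal. That touches an ethics-approved consent procedure, so it may cost more than a wording change, and items 1 to 4 do not depend on it.

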16.7 Planned final analyses

The primary analysis for the trial will occur once all patients have completed the 90-day follow-up assessment and corresponding outcome data has been entered onto the trial database and validated as being ready for analysis. This analysis will include data items up to and including the 90-day assessment and no further.

17 HEALTH ECONOMICS

A separate Health Economics Analysis Plan will be produced and will provide a more comprehensive description of the planned analyses. A brief outline of these analyses is given below.

17.1 Within-trial economic evaluation

The economic evaluation will compare the interventions from an NHS and Personal Social Services (PSS) perspective. A within-trial incremental cost-effectiveness (CEA) and cost-utility analysis (CUA) will be conducted at 90-day follow up to determine the cost per life year gained and cost per quality-adjusted life year (QALY) gained.

Resource use and costs: Health and social care resource use will be collected using study case report forms (using information from patient notes). Resource use will include intervention medication, number of days spent in hospital including length of stay in ICU, readmissions to hospital, including for acute clinical events such as stroke and MI. Resource use will be multiplied by unit costs obtained from standard (national) sources and healthcare providers.

Outcomes: The outcome measure for the cost-effectiveness analysis is survival at 90-days. For the cost-utility analysis, the EQ-5D-5L questionnaire will be administered to patients (or their carers) at hospital discharge, 60 and 90-days. EQ-5D-5L data will not be collected at baseline, as it will not be possible for this patient population to complete the questionnaire on admission to hospital. Therefore, we will use a previously published method and assume that the EQ-5D-5L score for all patients at baseline is zero, and the change in quality of life between baseline and hospital discharge is linear. Any patients who die within the 90-days will be assigned a utility of zero from date of death. The approach for estimating the baseline score will be explored in sensitivity analysis in two ways. Firstly, patients will be asked to provide their quality of life using the EQ-5D-5L at the 90-day data collection time point. Secondly, the utility value for unconscious will be assumed at baseline. The crosswalk value set will be applied to patient responses to obtain utility scores, in line with current National Institute for Health and Care Excellence (NICE) recommendations.

Analysis: As cost data is likely to have a skewed distribution (with high-cost outliers), a non-parametric comparison of means (using bootstrapping) will be undertaken. Where there are missing data on resource use or quality of life outcomes, multiple imputation techniques will be used to ensure that all trial patients are included in the final analysis. Adjustment for baseline covariates will focus on the same variables as outlined for the primary analysis. The robustness of the results will be explored using sensitivity analysis. Uncertainty will be explored through the use of cost-effectiveness acceptability curves (CEACs).

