9.1 Schedule of assessments

Table 1 - Schedule of Assessments

Procedure	Baseline (Day 0)	Day 1	Day 2	Day 3	Day7	ICU Discharge	Hospital Discharge	Day 60 (in hospital if necessary) (± 14 days)	Day 90 (± 14 Days)
Eligibility assessment	•								
Consent				•					
Randomisation	•								
Prescription of IMP by clinical team	•								
Demographics (medical records)	•								
Medical history (medical records)	•								
Cardiovascular	•	•	•	•	•				
Biochemistry	•	•	•	•	•				
AF resolution	•	•	•	•	•	•	•		
Expected Serious Adverse Events and Serious Adverse Events		•	•	•	•	•	•	•	•
Mortality and morbidity		•	•	•	•	•	•	•	•
Medications	•	•	•	•	•	•	•	•	•
Quality of life questionnaires (EQ-5D-5L)							•	•	•

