12.3 Patient completed questionnaires

The EQ5D-5L will be completed at hospital discharge, 60 days and 90-days.

Patients will be asked to complete the questionnaire with staff whilst in the hospital or over the telephone. The questionnaire should generally be completed by the patient alone but physical assistance in completing the form can be given by the research staff where appropriate. In such circumstances, questions are to be read to the patient verbatim and responses must not be led by research staff. EQ-5D-5L data will not be collected at baseline as it will not be possible for this patient population to complete the questionnaire on admission to hospital. Methods to account for this are outlined in section 17.

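### Sections 12.3 and 17.1 disagree on who may complete the EQ-5D-5L, and one of the two checks on the assumed zero baseline utility can be answered only by Day-90 survivors

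*Protocol*

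**What the plan says.** **Who answers.** Protocol Section 17.1 (Outcomes) states that "the EQ-5D-5L questionnaire will be administered to patients (or their carers) at hospital discharge, 60 and 90-days". Section 12.3 gives the site procedure: "The questionnaire should generally be completed by the patient alone but physical assistance in completing the form can be given by the research staff". It has patients complete the form with staff in hospital or by telephone, and it mentions no carer or proxy.

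**Baseline utility.** No baseline EQ-5D-5L is collected. Section 17.1 will "assume that the EQ-5D-5L score for all patients at baseline is zero", with linear change to hospital discharge. For deaths, "Any patients who die within the 90-days will be assigned a utility of zero from date of death". Two sensitivity analyses follow. The first: "Firstly, patients will be asked to provide their quality of life using the EQ-5D-5L at the 90-day data collection time point". The second: "Secondly, the utility value for unconscious will be assumed at baseline".

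**Schedule.** Table 1 (Section 9.1) has one quality-of-life row, marked at hospital discharge, Day 60 and Day 90. The visit lists in Section 9 and the time points in Section 12.3 agree with it.

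**Missing data.** The analysis paragraph of Section 17.1 plans multiple imputation so that every trial patient is included. Section 17 leaves further detail to a separate Health Economics Analysis Plan.

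**The concern.** Two separate matters affect the quality-of-life data.

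The first is the respondent rule. Inability to self-report is foreseeable in this trial. Section 5 expects most eligible patients to be sedated and ventilated at entry, Section 11.6 lists delirium as an expected event, and stroke is part of a secondary outcome in Section 8.2. A site that follows Section 12.3 has no instruction to approach a carer. Utility would then tend to be missing in the survivors whose health is worst, at all three time points that feed the base-case QALYs.

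The second is the first check on the zero baseline. Its information comes from a questionnaire given after randomisation, and only people alive at Day 90 can answer it. Survival to Day 90 is the primary outcome, whereas a test of a baseline assumption should not depend on outcome. The text does not say which period the answer refers to, or what value a patient who has died receives.

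**Working it through.** **1. Respondents, side by side.** Section 17.1 names patients or carers. Section 12.3 names patients, with research staff giving physical help. The word generally in Section 12.3 allows exceptions but supplies no alternative respondent. The two sections are not aligned.

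**2. Is there a separate baseline-recall item?** Table 1, the Section 9 visit lists and Section 12.3 each show a single EQ-5D-5L at Day 90. Section 12.3 refers to Section 17 for handling the missing baseline, and Section 17.1 offers only the sentence quoted above. No recall item is scheduled.

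**3. Design mortality (Section 16.1), reproduced first.**
- A fall from 20% to 15% gives HR = ln(0.85)/ln(0.80) = 0.728 (stated 0.73).
- Events by Schoenfeld: 4 × (1.960 + 1.282)² / (ln 0.73)² = 425; by Freedman, 432 (stated 426).
- Patients: 426 / 0.175 = 2434 (stated about 2430); 2430 / 0.95 = 2558, rounded to 2560 as stated.

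The rates of 20% and 15% are therefore the planning inputs.

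**4. Patients who cannot answer at Day 90.** 0.20 × 1280 + 0.15 × 1280 = 256 + 192 = 448, and 448/2560 = 17.5%.

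**5. Weight of baseline utility in the QALY.** With a linear path from baseline to discharge at day d, a baseline utility u contributes u × d / 2 / 365.25. Neither d nor u is in the documents, so ranges are assumed.
- d = 7: weight 0.0096. d = 30: weight 0.0411.
- Moving u from 0 to between 0.2 and 0.8 changes one patient's QALY by 0.0096 × 0.2 = 0.002 up to 0.0411 × 0.8 = 0.033.

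**6. Shift between arms.** Assume that only survivors (80% v 85%) receive the non-zero baseline and that deaths keep zero. The shift is 0.05 × the figures in step 5, or about 0.0001 to 0.0016 QALY. As an outer limit, discharge at Day 90 (weight 0.1232) gives 0.001 to 0.005.

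**7. Respondent gap, for scale only.** Suppose a share x of survivors cannot self-report, their utility is lower by g, and imputation recovers none of the gap. With discharge at day 21, mean QALY per survivor is overstated by x × g × (90 − 21/2) / 365.25.
- x = 0.05, g = 0.1: 0.0011.
- x = 0.30, g = 0.4: 0.0261.

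All of these inputs are assumed. The result is a level within an arm. It enters the between-arm difference only as far as x or g differs by arm.

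**The case against.** The strongest reply has five parts.

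- **The base-case baseline is intact.** It is zero for everyone, deaths stay in at zero utility, and the unconscious-value check does not depend on survival. This stands. A reader might infer that the trial's QALYs are skewed towards the fittest survivors. The documents do not support that, because the Day-90 issue is confined to one sensitivity analysis.
- **The Day-90 sentence may mean recall.** It reads at least as well as a retrospective question about baseline health. This also stands, so it cannot be asserted that the check imports any arm difference in current Day-90 utility. On either reading, however, only survivors can answer, and a recall question would need its own wording and schedule entry.
- **Imputation may cope.** Stroke events, delirium and SOFA components are collected and could inform it. Bias needs missingness that still depends on the unseen utility given those predictors, which the documents neither show nor exclude. It would go too far to say that imputation will overstate QALYs in the arm with more disabled survivors. Imputation could also give decedents a baseline value, which would change step 6.
- **The Health Economics Analysis Plan is still to come.** It can settle the handling of decedents and the imputation model. It cannot recover carer answers or a recall item that sites were never told to collect.
- **Deleting the Day-90 check is a preference.** Agreed. Defining it and treating it as supportive is enough.

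**Conclusion.** The point holds as two limited defects. First, Sections 12.3 and 17.1 give different respondent rules. Following Section 12.3 creates a risk of health-related missing utility in the base-case QALYs. Second, one of the two baseline sensitivity analyses depends on survival to Day 90, with its reference period, its scheduled item and its value for decedents all unspecified. At the planning rates about 448 of 2560 patients (17.5%) could not contribute to it.

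The direction and size of any bias cannot be derived from the protocol, which gives no utilities, discharge times or self-report rates. The range of 0.0001 to 0.0016 QALY between arms rests on assumed stays of 7 to 30 days, assumed utilities of 0.2 to 0.8, and decedents kept at zero. The matter is confined to the economic evaluation. The respondent rule is the more pressing part, because answers not collected now cannot be obtained later.

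**What to change.** **Section 12.3.** Align it with Section 17.1: use the proxy version of the EQ-5D-5L at hospital discharge, Day 60 and Day 90 when the patient cannot respond, and record who answered. The cost is a wording change, one respondent-type field and proxy completion within contacts already planned. The downside is some mixing of proxy and self-report, which the field allows analysts to examine.

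**Section 17.1.** State that the current-state Day-90 score is not used as baseline. Test the zero assumption with fixed values (the unconscious value already planned plus a stated range), applied identically to every randomised patient including those who die. If a Day-90 recall question is kept, add it to Table 1 and Section 12.3 as a separate item referring to baseline, state the value used for decedents, and label the analysis supportive. The fixed-value tests need no new data. A retained recall item adds one short questionnaire at an existing visit.
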